7 DATA PROCESSING

The results of the proposed clinical trial will be analysed descriptively by describing the antitumour effect, any adverse effects and the patients' quality of life after treatment of the primary liver tumours.

8 STATISTICAL ANALYSIS

All data will be entered into a Microsoft Access 2010 database, which will be used for all calculations except for statistical analysis, which will be performed with GraphPad Software (La Jolla, CA, USA). The log-rank (Mantel-Cox) test will be performed on the Kaplan-Meier estimates. A chi-squared test will be used for the statistical comparison of response according to tumor location. A two-tailed P value less than 0.05 will be considered to be statistically significant.

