1 PURPOSE OF THE STUDY

The purpose of this clinical study is to evaluate the safety and efficacy of bleomycin-based electrochemotherapy (ECT) in treating primary liver tumours in a phase I and II clinical study.

This will be achieved by:

- applying treatment in a controlled manner based on pre-clinical and clinical experience obtained in the ESOPE project;
- evaluating the procedures and results achieved;
- preparing standardized procedures;
- disseminating these new approaches to treatment using written and audio-visual materials, as well as by attending and organizing expert meetings.

The study is designed as an institutional study (at the University Medical Centre Ljubljana) conducted in cooperation with the Institute of Oncology Ljubljana and the Faculty of Electrical Engineering (University of Ljubljana), as well as an industrial partner, IGEA s.r.l., Carpi, Italy, which will provide technical support for the study. In phase I, 10 patients will be included in the study, and in phase II (i.e. the extension of the study), an additional 15 patients who meet the inclusion criteria will be included.

The study will be carried out within the P3-0003 “Razvoj in ovrednotenje novih terapij za zdravljenje malignih tumorjev” (Development and Evaluation of New Therapies for Treating Malignant Tumours) research programme headed by [name], PhD.

Principal investigators:

[name], MD (surgeon)
Assist. [name], MD, PhD (surgeon)

Study coordinators:

[name], PhD (researcher)
[name] [name], PhD (gastroenterologist)

Coordinators of the clinical part of the study:

Head physician [name] (surgeon)
Assist. [name], (surgeon)

Colleagues:

University Medical Centre Ljubljana

[name] (gastroenterologist)
[name] (radiologist)
[name] (surgeon)
Assist. [name] (surgeon)
Assist. [name], PhD (surgeon)
Head physician [name] (cardiologist)

Institute of Oncology Ljubljana

[name], PhD (surgeon)
Assist. [name] (surgeon)
[name] (surgeon)
[name] (research nurse)

[name] [name], PhD (researcher)

Faculty of Electrical Engineering, University of Ljubljana

[name], PhD (researcher)

[name], PhD (researcher)

[name] (researcher)

[name] (researcher)

[name] (researcher)

[name] (researcher)

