4 TREATMENT PLAN

Where there are liver tumours (up to 3 cm in maximum diameter) with the lower edge located up to 3 cm below the liver capsule, ECT using short-needle electrodes with a hexagonal geometric arrangement will be performed in line with the standard surgical procedures for treating cutaneous and subcutaneous tumours/metastases with ECT.

Where there are larger liver tumours (up to 5 cm) located near the vena cava or along large hepatic or portal veins, ECT using long-needle electrodes with an arbitrary geometric arrangement will be performed. Using numerical modelling, we will prepare a treatment plan to determine the optimal position of the electrodes and the required electric current voltage for the optimal electroporation of the target tissue. The preparation of a treatment plan using numerical modelling will take place in two basic steps (see below) based on radiological images captured up to 2 weeks before the procedure.

1. Decomposing medical images and constructing a model:
 - importing medical radiology images into an appropriate program,
 - determining important areas,
 - pretreating and decomposing images,
 - constructing a 3D model.
2. Planning treatment:
 - The 3D model will be supplemented with electrodes supplying electroporation pulses, as well as with corresponding tissue properties and boundary conditions based on the calculation using the finite element method and the calculation processed by automatic algorithms for determining the criterion function,
 - the possibility of statistical and probability functions to determine the probability of electroporation will be examined, the effect probability being a function of the electric field strength applied.

[figure not shown]

Figure 1: Schematic representation of electrode placement in the middle and the periphery of a metastasis in healthy liver tissue.

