5.2.3 Electroporation Pulses

- Between each pair of electrodes, 8 rectangular electroporation pulses (length: 100 μ s) will be supplied to the tumours in two sequences, each containing 4 electroporation pulses of reversed polarity and a repeating frequency of 1000 Hz.
- The delivery of individual pulse sequences will be synchronized with the occurrence of successive heartbeats.
- When using long-needle electrodes with an arbitrary geometric arrangement, the voltage of the electroporation pulses for each electrode pair will be determined on the basis of

numerical modelling, and when using short-needle electrodes with a fixed hexagonal geometric arrangement, a voltage of 730 V will be supplied.

- If excessive electric current (> 50 A) makes it impossible to supply a sufficiently high voltage, a larger number of lower-voltage electroporation pulses will be supplied.

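### The unadjusted test of response by tumour location cannot credit a difference to location alone, because the protocol ties location to electrode type, voltage rule and planning and, more loosely, to lesion size

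*Combined protocol and SAP*

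**What the plan says.** The only test that section 8 names for response is this: "A chi-squared test will be used for the statistical comparison of response according to tumor location". The threshold follows: "A two-tailed P value less than 0.05 will be considered to be statistically significant". The section does not say whether location means depth, closeness to large vessels or something else. It gives no stratification, adjustment or limit on interpretation.

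Elsewhere the protocol makes position part of how a lesion is treated:

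- **Section 2, Planning ECT Treatment:** electrode type depends on both the location and the measured size of the nodule.
- **Section 4, short needles:** "Where there are liver tumours (up to 3 cm in maximum diameter) with the lower edge located up to 3 cm" below the capsule. These lesions follow the standard procedure for skin tumours.
- **Section 4, long needles:** "Where there are larger liver tumours (up to 5 cm) located near the vena cava or along large hepatic or portal veins". These lesions get an individual plan from numerical modelling.
- **Section 5.2.2:** electrode type depends on depth alone, with the cut at 3 cm below the capsule and no condition on size or vessels.
- **Section 5.2.3, voltage:** "when using short-needle electrodes with a fixed hexagonal geometric arrangement, a voltage of 730 V will be supplied". For long needles the voltage of each electrode pair comes from the model.

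On numbers, section 1 says "In phase I, 10 patients will be included in the study", and in phase II "an additional 15 patients who meet the inclusion criteria will be included". Section 7 calls the analysis descriptive.

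**The concern.** A comparison by location is of real interest here. Section 2 gives safety in hard-to-reach sites as an aim and explains that tumours by large veins respond poorly to radiofrequency ablation. A reader will want to know whether ECT does as well there as elsewhere.

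The crude test cannot answer that. Lesions in different positions may also differ in electrode, voltage rule, planning and size. A difference could come from any of these. The reverse is also possible: a true deficit near vessels could be hidden if individually modelled treatment makes up for it. The trial could then report a location effect that is not one, or give false reassurance.

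**Working it through.** The plan gives no effect size or power for this test, so there is no figure to reproduce. The only count is 10 + 15 = 25 patients.

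**Step 1. How closely is location tied to treatment?**

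| Meaning of location | Link to electrode, voltage rule and planning | Link to size |
|---|---|---|
| Depth below the capsule | Complete under section 5.2.2 | Associated under section 4; no size condition in 5.2.2 |
| Closeness to large vessels | Partial: a shallow lesion up to 3 cm beside a vein fits the short-needle rule; a deep lesion away from veins fits the long-needle rule of 5.2.2 | Associated under section 4; inclusion criterion 3 admits smaller tumours in difficult locations |

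**Step 2. Partial overlap (closeness to vessels).** All rates here are assumptions. Location has no effect. Response is 90% in small lesions (up to 3 cm) and 60% in large ones. Of small lesions 10% are vessel-adjacent, and of large lesions 80%. With 12 small and 13 large lesions, the expected figures are:

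- Adjacent: 12 × 0.10 + 13 × 0.80 = 1.2 + 10.4 = 11.6 lesions. Response = (1.2 × 0.90 + 10.4 × 0.60) / 11.6 = 7.32 / 11.6 = 63.1%.
- Not adjacent: 10.8 + 2.6 = 13.4 lesions. Response = (10.8 × 0.90 + 2.6 × 0.60) / 13.4 = 11.28 / 13.4 = 84.2%.
- Crude difference: 84.2 − 63.1 = 21.1 points, with no location effect at all.

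Simulated rejection rates of the uncorrected Pearson test at two-sided 0.05, with lesions treated as independent:

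| Small / large lesions | 90% v 60% | 90% v 70% |
|---|---|---|
| 12 / 13 | about 24% | about 14% |
| 20 / 20 | about 35% | about 20% |
| 25 / 25 | about 43% | about 24% |

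Repeat simulations move these by about one percentage point. Without the link to size the rate would be about 5%.

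**Step 3. Full overlap (depth).** Take 80% for short needles, the background response rate quoted in section 2 for liver metastases, and assume a rate for long needles. With 12 v 13 lesions, exact enumeration gives rejection in 18%, 33% and 53% of trials when the long-needle rate is 60%, 50% and 40%. It is about 5% when the rates are equal. At 75% concordance between location and electrode type, the 80% v 60% case falls to 8%.

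**Step 4. What can adjustment recover?** With balanced groups and concordance *a*, the correlation between location and electrode type is φ = 2*a* − 1. The information left about location is roughly 25 × (1 − φ²) lesions:

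- *a* = 100%: 25 × (1 − 1²) = 0
- *a* = 95%: 25 × (1 − 0.9²) ≈ 5
- *a* = 90%: 25 × (1 − 0.8²) = 9
- *a* = 75%: 25 × (1 − 0.5²) ≈ 19

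If location is depth, nothing is left to estimate.

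**Step 5. Does stratifying by size help?** In the step 2 setting, an exact test stratified by size class brings the 24% below 5%. That is because response there depends on size class only. If electrode type matters within a size class, stratifying by size does not remove its effect. The test detects a true 30-point location effect in only about 10% of trials at 12 / 13 lesions and 29% at 25 / 25. These figures shift by a few points with the assumed rates and the form of exact test.

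**The case against.** The strongest case against is that the analysis is described as descriptive, location is a side comparison in 25 patients, and the chi-squared test is a valid test of association. No passage says that a difference would be read as an effect of location itself. All of that stands, and it limits the point to interpretation and missing stratification. It does not dispose of it, because section 8 adds a significance threshold to the comparison with no caveat.

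Several stronger readings are tempting, and the documents do not support them:

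- **Location decides lesion size.** Section 2 makes size a separate criterion, and inclusion criterion 3 expects smaller tumours in difficult places. Size is associated with location, not fixed by it.
- **No difference could ever be credited to location.** That follows only if location means depth. For closeness to vessels the overlap is partial, and some information may remain.
- **The plan itself regards electrode type as a strong confounder.** Section 2 calls the electric field distribution an important predictor of success. It does not say that the two electrode types give different coverage, and modelling may even out field delivery.
- **The high-current fallback follows location.** Section 5.2.3 states it generally: "If excessive electric current (> 50 A) makes it impossible to supply a sufficiently high voltage, a larger number of lower-voltage electroporation pulses". It is not limited to long needles.

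It is also fair to object that the rejection rates rest on assumed response rates and overlap. A continuity correction would lower them: the 18% in step 3 becomes about 9%.

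**Conclusion.** The concern holds in a limited form. Section 8 plans a crude comparison by an undefined location, while the protocol ties location to electrode type, voltage rule and planning and, less strictly, to size. A difference cannot be credited to location alone. The aliasing is complete if location is depth and partial if it is closeness to large vessels.

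The size of the problem is not known from the documents. On the assumed partial overlap, a size effect alone makes the crude test reject in about 24% to 43% of trials at 90% v 60%, and 14% to 24% at 90% v 70%. This assumes independent lesions, with 25 in all (one per patient) or 50, and the uncorrected test. Weaker overlap or smaller effects give less: 8% at 75% concordance with 80% v 60%.

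Sections 4 and 5.2.2 state different electrode rules: size with depth or vessel position in one, depth alone in the other. Until they are reconciled, the degree of aliasing cannot be settled.

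**What to change.** In section 8:

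1. Define location. Class each lesion from the planning images, before ECT, as adjacent or not adjacent to the vena cava, hepatic or portal veins.
2. Report response, with intervals, by location within size class (up to 3 cm / over 3 cm) and electrode type.
3. Replace the crude chi-squared test by an exact test stratified by size class, labelled exploratory.
4. State that where a stratum holds only one location, or location coincides with electrode type, the report will give a combined location-size-electrode group difference and draw no conclusion about location.

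Separately, the electrode rules in sections 4 and 5.2.2 must be reconciled. Which rule applies is for the investigators.

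The cost is a change of wording and a few columns in the lesion table. Size and electrode type already arise from planning and treatment. The drawback is wider intervals and low power, as step 5 shows, so a non-significant stratified result must not be read as evidence that location does not matter. The tabulation and the limit on interpretation do most of the work.

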The first recorded clinical case of treating a deep-seated tumour with ECT involved treating melanoma metastases in thigh muscles.⁷ Experience in treating other types of soft tissue tumours with ECT is good but limited to a few clinical cases and studies involving a small number of patients.⁸⁻¹¹ In addition to treating deep-seated soft tissue tumours, ECT is used to treat deep-seated tumours in the internal organs. Brain and liver metastases have already been shown to be effective targets of ECT.¹²⁻¹⁴ The results of a clinical study on electrochemotherapy used to treat liver metastases of stage I and II colorectal cancer prove the safety and efficacy of this approach. Preliminary results have already been published for the case of one patient, where the treatment procedure is described in detail.¹⁴ Conclusions on safety and efficacy are in the process of publication for the first 17 patients treated with electrochemotherapy. No serious side effects attributable to ECT were observed in the study, and the efficacy results suggest an 80% response from the treated metastases to ECT, which is comparable to that of skin metastases.

Treatment of Primary Malignant Liver Tumours

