6.1 Effects of Treating Primary Liver Tumours Using ECT

- Early treatment effects will be assessed using DCE-US or CT based on changes in tumour blood flow after ECT compared to the pre-ECT blood flow.

- Late effects will be assessed based on modified RECIST criteria, taking into account the change in the size and density of the treated tumour nodules before and after ECT. These will be assessed based on CT perfusion imaging; the volume of the metastases will be calculated using the formula $V = \frac{a \times b^2 \times \pi}{6}$, where a is the shorter and b the longer metastasis diameter.

Based on the assessment of the late ECT effects, the response to treatment will be evaluated in line with the WHO classification:

- Complete response (CR): complete disappearance of the tumour nodule
 - Partial response (PR): reduction of the tumour nodule size by more than 50%
 - No change (NC): decrease in tumour nodule size by less than 50% or an increase in the tumour nodule size by less than 25%
 - Progressive disease (PD): growth of the tumour nodule by more than 25%
- The direct effect will be assessed by histological analysis of those metastases that are surgically removed.
 - EORTC Quality of Life questionnaire according to the QLQ C30 standards

EXAMINATION/TEST	Screening period until D -14	D -1	D7	D30	D60	D90	D120
clinical examination, anamnesis	X	X	X	X	X	X	X
ECG	X	X					
DCE-US	X			X	X		X
CT perfusion / MRI	X			X			X
Blood count	X	X	X				
Coagulation tests	X	X	X				
Biochemical blood analysis	X	X	X	X	X		X
EORTC QLQ C30 questionnaire	X		X	X			

*D = day

6.2 The Effects of Electroporation Pulses, BLM or ECT as a Whole on Cardiac Function

- To study the short-term effect, we will use the ECG signal captured during surgery, which will cover the period before, during and immediately after ECT, including BLM injection and electroporation pulses.
- To study possible late and/or long-term effects, the ECG signal will be recorded using a standard Holter system in 24-hour periods immediately before and after surgery. 5-10 patients will be included.

ECG recordings will also be performed on 10-15 patients who will undergo abdominal surgery without ECT at the Department of Abdominal Surgery, University Medical Centre Ljubljana.

6.3 Recording ECT Adverse Effects will be Performed According to the Criteria of the National Cancer Institute (NCI)

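### Section 8 compares an ordered response scale (CR, PR, NC, PD) by tumour location with a chi-squared test; an exact ordinal test would suit about 25 patients better, with a gain that depends on unstated assumptions

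*Combined protocol and SAP*

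**What the plan says.** The response scale is in Section 6.1. It runs from "Complete response (CR): complete disappearance of the tumour nodule" through partial response and no change to "Progressive disease (PD): growth of the tumour nodule by more than 25" per cent. The middle cut-points are a 50% reduction and a 25% increase. All four categories are therefore cut from one size-change scale, and their order is built into the definition. Grading is by nodule, "taking into account the change in the size and density of the treated tumour nodules before and after ECT".

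The test is in Section 8: "A chi-squared test will be used for the statistical comparison of response according to tumor location". The threshold follows: "A two-tailed P value less than 0.05 will be considered to be statistically significant". Section 8 names no ordinal or trend version, no responder cut-point, no definition of the location groups and no unit of analysis. It also plans a log-rank test on Kaplan-Meier estimates.

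The sample is in Section 1: "In phase I, 10 patients will be included in the study", and in phase II "an additional 15 patients who meet the inclusion criteria will be included". That makes 10 + 15 = 25 patients. Section 7 describes the analysis as descriptive.

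**The concern.** Pearson's chi-squared test treats the columns of a table as unordered labels. Shuffling CR, PR, NC and PD leaves its P value unchanged. With two locations it spreads its power over (2 − 1) × (4 − 1) = 3 degrees of freedom, whereas the natural question, whether response is better in one location than another, needs one.

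A second weakness is that the chi-squared approximation is unreliable when expected counts are small, as they must be here. The two are separate: an exact version of the unordered test repairs the approximation but still ignores the order.

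What is at stake is the sensitivity of the only planned comparison of response between locations. Section 2 makes treatment in hard-to-reach locations part of the study's aim, and Section 8 attaches a significance rule to the comparison.

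**Working it through.** **Inputs from the documents.** N = 25 patients (Section 1); two-sided 0.05 (Section 8); four ordered categories (Section 6.1). There is no stated power, effect size or sample-size calculation to reproduce. The only response rate for liver tumours is from an earlier metastasis study (Section 2: "the efficacy results suggest an 80% response from the treated metastases to ECT"). It is not split into CR and PR and is not a design assumption.

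**Assumed inputs.** One independent response per patient; two locations of 12 and 13 patients; category distributions as shown below.

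**Step 1: expected counts.** E = (location size) × (category proportion). With CR/PR/NC/PD = 50/30/15/5 in both locations:
- 12 patients: 6.0, 3.6, 1.8, 0.6
- 13 patients: 6.5, 3.9, 1.95, 0.65

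Six of eight cells are below 5.

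**Step 2: the tests.**
- Unordered: X² = Σ(O − E)²/E.
- Ordinal: W = sum of midranks in the first location, compared with its null mean 12 × 26/2 = 156.
- Exact P, either test: given the category totals m_j, a table with counts t_j in the first location has probability ΠC(m_j, t_j)/C(25, 12). P is the total probability of tables at least as extreme, by X² or by |W − 156|.
- Power: the multinomial probability of all tables with P ≤ 0.05, over all 455 × 560 = 254,800 possible pairs of location results.
- The yes/no tests are Fisher's exact test with the usual two-sided P.

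**Step 3: exact power.** The first distribution belongs to the location with 12 patients.

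| CR/PR/NC/PD | Unordered, four categories | Ordinal | Gain (points) | CR+PR yes/no | CR v not-CR |
|---|---|---|---|---|---|
| 60/25/10/5 v 25/35/25/15 | 30.5% | 43.8% | 13.3 | 19.6% | 41.6% |
| 70/20/5/5 v 25/30/25/20 | 50.6% | 66.7% | 16.1 | 40.0% | 62.7% |
| 70/20/7/3 v 30/40/20/10 | 38.0% | 49.5% | 11.5 | 12.6% | 51.2% |
| 50/30/15/5 in both (null) | 4.3% | 4.2% | – | 2.5% | 4.3% |

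The unordered and ordinal tests have almost equal null rejection, so the gain of about 12 to 16 points comes from using the order. If the better-responding location has 13 patients instead, the gains are about 10 to 14 points.

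The ordinary large-sample chi-squared test, as planned, has 28%, 48% and 34% power in the three scenarios, 2 to 4 points below its exact version. Its null rejection is 3.5%.

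**Step 4: range over other assumptions.** Simulation (40,000 trials per scenario, N = 25) compared the ordinary chi-squared test with the tie-corrected Wilcoxon test under proportional-odds shifts.
- 80% CR+PR, 12 v 13: about 13-15% v 7-9% at odds ratio 2; 28-30% v 16-17% at 3; 43-44% v 26% at 4; 64-65% v 43-44% at 6.
- Smallest gain: 12.4% v 10.5%, about 2 points (25% in each category, 6 v 19, odds ratio 2).
- Largest gain: about 22 points (12 v 13, odds ratio 6).
- Three locations of 8, 8 and 9: about 11 to 21 points.

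**Step 5: patterns that are not a shift (exact, 12 v 13).**
- 50/30/15/5 v 15/65/15/5: ordinal about 26%, unordered about 42%.
- 50/40/5/5 v 50/10/20/20: ordinal about 10%, unordered about 39%.

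These are averages over which location has 12 patients.

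**Step 6: several nodules per patient.** Assuming two nodules per patient in the same location and a latent correlation of 0.3 to 0.5, a Wilcoxon test that treats nodules as independent rejects about 8-9% of the time under the null.

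**The case against.** The strongest objection is that Section 8 never says a four-category table is tested. Section 2 quotes response as a single proportion, so a responder/non-responder table is a natural reading, and it has no order to ignore. This stands: the criticism of lost order is conditional. The recommendation still has some support on that reading, because in the three scenarios the ordinal test beats a CR+PR split. A reader might infer that any collapsing loses more still. That is not so: a CR v not-CR cut recovers most of the gap and edges ahead in the third scenario.

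A reader might also take 12 to 16 points as a property of this trial. The documents give no effect size, category distribution, location groups or group sizes, and all three scenarios are shifts, which favour the ordinal test. Step 5 shows that the ranking can reverse.

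Calling a test exact does not make it valid for clustered nodules. Section 3.1 allows for patients with many tumours, so this also stands and has to be part of the fix.

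Finally, Section 7 is descriptive, no decision is tied to the location comparison, and a log-rank test is planned too, so this is not the sole planned test. Power is limited either way: at odds ratios up to 4 the ordinal test reaches at most about 44%. The impact is modest.

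**Conclusion.** The point holds in conditional form. The response scale is ordered, and an ordinary chi-squared test on all four categories would ignore that order and rest on expected counts mostly below 5. If locations differ by a better-to-worse shift, an ordinal test gains about 2 to 22 points of power over the four-category test, and 12 to 16 points in the three enumerated scenarios at 12 v 13. It also beats the CR+PR split in those scenarios, but not reliably the CR v not-CR cut.

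These sizes rest on assumed distributions, location splits and independent responses. The documents do not support a fixed loss of power for this trial, nor a claim that the planned test invalidates its results. This is a worthwhile, inexpensive improvement to an exploratory comparison.

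**What to change.** In Section 8:

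1. Define the location groups, and state that response by location is analysed on the ordered scale CR > PR > NC > PD.
2. Compare two locations with the exact Wilcoxon-Mann-Whitney test, or more than two with the exact Kruskal-Wallis test, at two-sided 0.05.
3. Use one response per patient, chosen by a rule fixed before the data are seen, or permute at patient level when a patient has several nodules. Say how patients with nodules in more than one location are handled.
4. Report the objective response rate (CR+PR) in each location and the difference with a 95% confidence interval, on the same unit of analysis.
5. Show the full location by category table, so that a non-monotone pattern is visible.

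The cost is a few lines of text, with no new data and no extra patients. The team should confirm that the named software computes exact P values with heavy ties and can permute by patient, or name another package. The statistical price is lower power against non-monotone differences, for example about 26% v 42% in Step 5.
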